**Topical Antibiotic Irrigation (Gentamicin) in Prophylaxis of Midfacial Fracture
Surgical Wounds**

NCT 03483363

Version Date: 05/08/2020

Protocol Title:	Topical Antibiotic Irrigation (Gentamicin) in Prophylaxis of Midfacial Fracture Surgical Wounds
Principal Investigators:	[name]
Co-Investigators:	[name], [name], [name], [name]
Faculty Advisor:	[name], [name], [name]
Population:	Adult Patients admitted to Memorial Hermann Hospital (MHH) for treatment of Midfacial fractures
Number of Sites:	Memorial Hermann Hospital
Study Duration:	Prospective trial, 4 years
Subject Duration:	Associated hospital stays, Follow up to eight weeks postoperatively

General Information

The purpose of this study is to evaluate the use of topical antibiotic irrigation (Gentamicin) and its ability to reduce surgical site infections in midfacial fracture surgery compared to sterile normal saline (NS).

Background Information

The Centers for Disease Control and Prevention estimates that 16 million surgical procedures were performed in acute care hospitals in the United States in 2010 (CDC). A recent study found that surgical site infections (SSIs) accounted for roughly 31% of all hospital acquired infections (HAIs) (Magill). The overall infection rate for traumatic midfacial fracture is about 9% (Lauder). Current regimens applied for prevention of SSIs include: preoperative antiseptic preparation and systemic parenteral antibiotic prophylaxis, intraoperative aseptic techniques, and postoperative incision care (Mangram).

Intraoperative topical antibiotic irrigation intraoperatively is becoming more prevalent, supplementing the recommended use of intravenous prophylactic administration of antibiotics prior to surgery (Andreasen). Typical irrigation agents include sterile saline, Gentamicin, chlorhexidine gluconate, betadine, Bacitracin, and hydrogen peroxide. The majority of prospective references reviewed were limited to orthopedic, abdominal, ocular, breast, dermatologic, and cardiothoracic surgeries with a significant lack of sources referencing maxillofacial surgeries (McHugh). The available reports on the use of topical antibiotic irrigation in prophylaxis of facial surgical wounds is insufficient.

Objectives

- Does the use of topical antibiotic irrigation (Gentamicin) reduce surgical site infections in midfacial fracture surgery compared to sterile NS?

Study Design

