- Prospective randomized trial: All groups will receive standard parenteral (IV) prophylactic antibiotic. In the control group, the fractures will be irrigated with sterile normal saline prior to closure. In the trial group, the fractures will be irrigated with Gentamicin topical antibiotic

(80mg diluted in 1L 0.9% NS) prior to closure. Patients will not receive postoperative oral antibiotics.

- Double blinded: Intraoperative irrigation will be concealed (saline vs Gentamicin) to the patient and the surgeon.
- Expected duration of study is about 4 years and subject participation is expected to be about 200.
- The primary outcome to be measured is the rate of surgical site infections. The main investigator ([name]) will determine SSI (evidence of infection: persistent swelling, fever, recurrent swelling, erythema, and purulent discharge). Statistical analysis plan will be multivariate: SSI, use of Gentamicin, type of fracture, past medical history, social history, days before surgery.
- Assessment of efficacy.
- Assessment of safety.

Gentamicin information – Topical use

- Please see separate package insert document for more detailed information
- A topical irrigation solution may be compounded by dissolving appropriate amount of Gentamicin injection or Gentamicin compounding powder in 0.9% Sodium Chloride injection or sterile water for injection for a final concentration of 0.08mg/mL.
- This drug is contraindicated in those individuals with a history of previous hypersensitivity or allergic reaction to it
- Dosage form: 8mg/Vial, injection
- Maximum dosage: 5 mg/kg/day IV/IM is FDA-approved maximum. There is no maximum dose stated for ophthalmic or topical administration.
- There is no premixed solution. The Gentamicin is obtained at the hospital pharmacy and is mixed with 0.9% normal saline in the operating room by the scrub tech under sterile condition with nurse practitioner supervision ([name]) in order to maintain the blind. 80mg will be used per patient.

Study Population

- Inclusion: All patients 18 years of age and older who are planned for open reduction internal fixation of midfacial fractures as part of standard of care
- Exclusion: Infected surgical sites, allergies to Gentamicin
- Recruitment: Will recruit all patients who are admitted to Memorial Hermann hospital at Texas Medical Center

Study Procedures

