- Expected number of visits will be about 5. First visit will be for evaluation in emergency department. Second visit will be for surgery. Also, patient will be monitored in the hospital postoperatively and will be seen for follow up in clinic.
- Every case included will be randomized based on lottery system for intraoperative sterile saline vs Gentamicin irrigation
- Every administered agent will not be known to patient or surgeon
- Patient will be then followed and monitored as per standard of care (inpatient monitoring, clinic follow up after discharge, last follow up at 8 weeks)
- The following will be considered evidence of infection: persistent swelling, fever, recurrent swelling, erythema, and purulent discharge

- Patient information will be gathered to evaluate the type of surgery, medical history of patient, research intervention of irrigation, types of antibiotics used, inpatient recovery, and follow up care. The information will be recorded an encrypted separate electronic document to ensure protection of patient information: secureshare.uth.tmc.edu

Data and Safety Monitoring

- Adverse events are not expected
- Data will be collected and kept by designated research assistants, [name] and [name].
- Data will be kept on the secured website: secureshare.uth.tmc.edu
- Interpretation of all information and results to be calculated at the conclusion of the last follow up of the last case included in the study to reduce bias
- At the conclusion of the study, data kept will have no patient information but still will be stored in the secured location

Statistics

- The aim of this study is to mainly compare the statistical outcomes between each group. Once the data tabulation is completed, other statistical analysis may be pursued after consultation with the statistician in UT Health.
- Prior to data requisition, UTHealth statisticians, [name] and [name], were consulted for sample size calculation assistance.
- Given the prevalence of surgical wound infection in our target population is 9%, with a sample size of 100 per group (200 total), a type 1 error rate of 0.05 and a type 2 error rate of .80 (80% power), we will be able to detect a reduction of 9 percentage points, from 10% in the saline group to 1% in the topical antibiotic group.

Ethics

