- IRB approval will be sought from CPHS. Start of project will be conducted only after all permissions and approval are granted. Chart reviews and data collection will be conducted only after all permissions and approval are granted
- Consent will be obtained from each patient using standard consent forms for the specific surgery. A separate research consent form will be completed by each patient discussing the research study specifically.
- Once IRB approval is granted, additional application to the respective hospital will be submitted individually to the respective research office and the offices of the respective chiefs of staff

Data handling and record keeping

- Data will be collected using medical record numbers avoiding any specific patient's identifiers
- Data will be secured in secureshare.uth.tmc.edu or similar UT Health approved storage media

Quality control and assurance

- Data collections will be performed by research assistants

Publication Plan

- Data and conclusion will be shared internally for quality improvement
- Data will be also shared in local and national professional meetings
- Future publications in professional journals

Attachments

- See specific data collection outline below

Data Collection

MRN		
Age		
Gender		
PMHx		
Medications		
Allergies		
Social history		
Injuries		
Type of fracture		
Days before Surgery		
Gentamicin		
No Gentamicin		
Post-op Hospital Course		
Follow up #1		
Follow up #2		
Infection		
No Infection		
Other Complications		

References

2. (CDC) "Surgical Site Infection (SSI) Event." *Centers for Disease Control*, Jan. 2017, Web: <https://www.cdc.gov/nhsn/pdfs/pscmanual/9pscscurrent.pdf>.

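### Safety is listed as part of the design, but harms other than infection are left to undefined open fields, so a report of no adverse events would be weak evidence

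*Combined protocol and SAP*

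**What the plan says.** Study Design lists "Assessment of safety" as a bullet of its own, next to the one for efficacy, and adds nothing to it. The section headed Data and Safety Monitoring has one sentence on harms: "Adverse events are not expected". Its other bullets deal with who holds the data, where they are stored, and when they are interpreted. On timing it says: "Interpretation of all information and results to be calculated at the conclusion of the last follow up of the last case included in the study", and gives reduction of bias as the reason.

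The protocol does name one risk. The gentamicin information section states: "This drug is contraindicated in those individuals with a history of previous hypersensitivity or allergic reaction to it", and Study Population excludes patients allergic to the drug.

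The places where a harm could be recorded are in the Data Collection outline at the end: "Post-op Hospital Course", two follow-up rows, and "Other Complications". Each is a bare label. Study Procedures provides for "inpatient monitoring, clinic follow up after discharge, last follow up at 8 weeks" as standard of care. The analysis described in Study Design is a multivariate model of infection. Neither it nor the Statistics section mentions a safety table.

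**The concern.** A trial that lists safety as something it assesses should say what it looks for, when, and how the results will be shown. Here the only statement on adverse events is an expectation that there will be none, and recording depends on whoever fills in an open line.

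The difficulty is one of interpretation. An empty complications line may mean that the patient was asked and had no event, that nobody asked, or that something was seen but not thought worth entering. The form cannot separate these. If the report then states that there were no adverse events, the statement will carry less information than it appears to. This cannot be reliably repaired at analysis, because data that were not collected prospectively would have to be reconstructed from charts. The one harm that the protocol names, hypersensitivity, has no field asking whether it occurred in an enrolled patient.

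**Working it through.** **Setting the sections side by side.**

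- Study Design: safety is named, with no endpoint.
- Data and Safety Monitoring: no adverse-event definition, event list, severity grade or reporting route.
- Gentamicin information: one named risk, hypersensitivity.
- Data Collection: open rows that can hold a complication, with no named event, date or severity. The allergies row sits among the history items, ahead of the treatment rows, so it reads as a baseline item.
- Analysis: infection only.

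**The plan's own figure.** The documents give no figure for safety. Their one calculation is 80% power for infection at 10% versus 1% with 100 per group and a type 1 error of 0.05. It reproduces with a two-sided pooled z-test:

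- SE under the null = sqrt(2 × 0.055 × 0.945 / 100) = 0.03224
- SE under the alternative = sqrt((0.10 × 0.90 + 0.01 × 0.99) / 100) = 0.03161
- Power = Φ((0.09 − 1.96 × 0.03224) / 0.03161) = Φ(0.848) = 80.2%

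This confirms 100 per group as the planned size but says nothing about harms.

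**What 100 gentamicin patients can show with complete recording.** With zero events in n patients, the exact upper limits are:

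- One-sided 95%: 1 − 0.05^(1/100) = 2.95%
- Two-sided 95% (Clopper-Pearson): 1 − 0.025^(1/100) = 3.62%

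The protocol states no dropout allowance. With 90 or 80 evaluable patients (assumed), the one-sided limit would be 3.27% or 3.68%. The chance of at least one event at a true risk of 1% is 1 − 0.99^100 = 63.4%. These figures follow from the sample size and would hold under perfect recording, so they are the baseline and not the size of the defect.

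**What incomplete recording adds.** Suppose each event is recorded with probability c, independently. Recorded events then have rate c × p, and zero recorded events bounds c × p at 2.95%, so the limit on p is 2.95% / c. The documents give no value for c. The values below are assumptions that show the range.

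| Share recorded (assumed) | One-sided 95% limit on true rate, 0 recorded in 100 | Chance of recording at least one event at true 1% |
|---|---|---|
| 100% | 2.95% | 1 − 0.99^100 = 63.4% |
| 50% | 2.95 / 0.50 = 5.9% | 1 − 0.995^100 = 39.4% |
| 25% | 2.95 / 0.25 = 11.8% | 1 − 0.9975^100 = 22.1% |

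**Comparison between arms.** Even with full recording, power is low. For 1% versus 5% (illustrative rates), the same z-test gives:

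- SE under the null = sqrt(2 × 0.03 × 0.97 / 100) = 0.02412
- SE under the alternative = sqrt((0.05 × 0.95 + 0.01 × 0.99) / 100) = 0.02396
- Power = Φ((0.04 − 1.96 × 0.02412) / 0.02396) = Φ(−0.304) = 38.1%

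Fisher's exact test gives 19.4%. A safety table should therefore be descriptive, with intervals, and not a test.

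**The case against.** The case for the plan as written is substantial. The outline does have places for harms: a line for other complications beside the infection rows, the hospital course, and two follow-ups. Patients in both arms are monitored in hospital and seen to 8 weeks, so staff can observe and enter a complication. What is attached is called an outline, and even the primary outcome appears in it only as a label, so the working form may hold more. The infection comparison does not depend on any of this.

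These points limit what can be claimed. A reader might infer any of the following, and the documents support none of them:

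- **That the form asks for no harms, or that a reaction is recorded only if someone volunteers it.** The open rows and the planned monitoring contradict this. What is missing is a prompt for any named event.
- **That no safety conclusion of any kind is possible.** Recorded complications in two randomized arms, with patient and surgeon blinded, allow a crude descriptive comparison. It is weak, not empty.
- **That the trial sets out to weigh benefit against harm.** The sole objective is "Does the use of topical antibiotic irrigation (Gentamicin) reduce surgical site infections in midfacial fracture surgery compared to sterile NS". The commitment to safety rests on the Study Design bullet alone.
- **That the end-of-study rule forbids acting on events during enrolment.** It concerns interpretation of results, to reduce bias, and does not bar reporting an event. The study is under IRB approval, and reporting duties may be set out elsewhere. The fair statement is that this document describes no reporting route.

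What remains is that the plan names safety, expects no adverse events, and does not make the assessment operational. Bare labels and general monitoring do not distinguish an absent event from a question not asked.

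**Conclusion.** The point holds in this limited form. It is a low-cost improvement that should be made, and it is no threat to the primary result. As written, the plan supports only a crude descriptive comparison of whatever complications are entered, and the absence of recorded events would be weak evidence of safety.

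Zero events in 100 gentamicin patients would leave a one-sided upper limit of about 3% at best, and about 6% to 12% if half to a quarter of events were recorded. The first figure assumes 100 evaluable patients and complete recording. The range rests on assumed recording shares that the documents neither give nor exclude. It illustrates the direction and possible size of the problem and does not estimate it.

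**What to change.** Replace the sentence on expected adverse events with prompted yes/no items, each with date and severity, completed in both arms. The minimum list is allergic or hypersensitivity reaction, wound complication other than infection, and any other event. Use the time points already on the outline: the post-operative hospital course (covering the operation itself) and the two follow-ups. An explicit no then replaces an ambiguous blank.

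State that serious events go to the investigator and the IRB as they occur, and that the rule deferring interpretation to the end of the study does not apply to them. Tabulate events by arm with exact 95% confidence intervals, including the upper limit where the count is zero.

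If this is not wanted, delete the safety item from Study Design and limit conclusions to efficacy.

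The cost is one form revision, one table and a few minutes at each existing time point. The safety statement will also read less favourably, because it will carry its upper limit.

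### The power sentence starts from a 9% infection rate but attaches its 80% power to an unexplained 10% saline rate; at 9% the same formula gives about 74% (79% by exact calculation for the chi-square test)

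*Combined protocol and SAP*

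**What the plan says.** All references are to the combined protocol and SAP.

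- **Background Information** cites a source for the rate: "The overall infection rate for traumatic midfacial fracture is about 9"%.
- **Statistics** makes that rate the premise of the power sentence: "Given the prevalence of surgical wound infection in our target population is 9"%. With 100 per group (200 in total), the sentence goes on to specify "a type 1 error rate of 0.05 and a type 2 error rate of .80 (80% power"), and concludes that "we will be able to detect a reduction of 9 percentage points, from 10% in the saline group to 1"% with gentamicin.
- **Study Design** describes the analysis only in outline: "Statistical analysis plan will be multivariate: SSI, use of Gentamicin, type of fracture", followed by history and timing variables. No test for comparing the two infection rates is named, and sidedness is not given anywhere.
- **Study Design** also describes the control arm: standard IV prophylaxis and saline irrigation, and "Patients will not receive postoperative oral antibiotics".

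**The concern.** One sentence contains two different infection rates. It opens with 9%, the only rate that the document supports with a citation, and reports power from 10%, which appears once and has no source. Nothing connects the two. The 10% is not rounded from an average over the arms either: the two planning rates average (10% + 1%)/2 = 5.5%.

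This sentence is the only basis given for enrolling 200 patients. If the saline rate is the 9% that the sentence itself assumes, the 80% does not follow from its premise, and a later null result would be read against a power figure that belongs to a different control rate. The mislabelled type 2 error in the same sentence adds to the confusion, although no number depends on it.

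**Working it through.** **Inputs.** From Statistics: n = 100 per group, type 1 error 0.05, power 80%, saline rate 10%, gentamicin rate 1%, premise 9%. Assumed, because the document is silent: a two-sided test, and all 100 patients per group analysed (no dropout allowance is stated).

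**Step 1. Reproduce the stated 80%.** The two-sided pooled z formula, without continuity correction, is

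power = Φ{ [d − 1.96·√(2·p̄(1−p̄)/n)] / √[(p₁(1−p₁) + p₂(1−p₂))/n] }, with d = p₁ − p₂ and p̄ = (p₁ + p₂)/2.

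At 10% versus 1%: d = 0.09 and p̄ = 0.055.
- Null term: 1.96 × √(2 × 0.055 × 0.945/100) = 1.96 × 0.03224 = 0.0632.
- Denominator: √[(0.0900 + 0.0099)/100] = 0.03161.
- Power = Φ[(0.0900 − 0.0632)/0.03161] = Φ(0.848) = **80.2%**.

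The formula also returns exactly 100 per group for 80% power, so it is a plausible guess at what was used.

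**Step 2. Same formula from the 9% premise.** At 9% versus 1%: d = 0.08 and p̄ = 0.05.
- Null term: 1.96 × √(2 × 0.05 × 0.95/100) = 1.96 × 0.03082 = 0.0604.
- Denominator: √[(0.0819 + 0.0099)/100] = 0.03030.
- Power = Φ[(0.0800 − 0.0604)/0.03030] = Φ(0.647) = **74.1%**.

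**Step 3. Could another formula lie behind the 80%?** Three other methods come within 2 points of 80% at 10% versus 1%, and all show a similar drop at 9% versus 1%: unpooled z, two-sided (81.3% to 75.2%); continuity-corrected z, one-sided (80.3% to 73.8%); and Boschloo's exact test, two-sided (80.5% to 72.4%). Some methods keep at least 80% at 9%, such as two-sided arcsine (82.4%) and one-sided pooled z (83.3%). At 10% these two give 88.0% and 87.9%, so they do not match the stated figure.

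**Step 4. Actual power of the test.** With about one infection expected in the gentamicin arm (100 × 1%), a normal approximation is rough. Exact power is the sum of Bin(x; 100, p₁) × Bin(y; 100, p₂) over all pairs (x, y) that the test declares significant at two-sided 0.05. The uncorrected chi-square test is the pooled z-test squared.

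| Saline vs gentamicin | Pooled z formula | Chi-square, exact power | Fisher's exact test, exact power |
|---|---|---|---|
| 10% vs 1% | 80.2% | 85.4% | 76.9% |
| 9.5% vs 1% | 77.3% | 82.3% | 72.6% |
| 9% vs 1% | 74.1% | 78.8% | 67.7% |

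Moving from 10% to 9% costs 80.2 − 74.1 = 6.1 points by the formula, 85.4 − 78.8 = 6.6 points for the chi-square test and 76.9 − 67.7 = 9.2 points for Fisher's test. Measured against the stated 80%, the position at 9% is 80 − 78.8 = 1.2 points short for the chi-square test and 80 − 67.7 = 12.3 points short for Fisher's test.

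**Step 5. Type 2 error.** Type 2 error = 1 − power = 1 − 0.80 = 0.20. The sentence prints .80 and then correctly puts 80% power in brackets, so this is a labelling slip.

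**The case against.** The strongest reply has three parts.

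*The sum is right and the rates are in plain view.* The 80% is correct for 10% versus 1%, and the sentence states both rates. This stands: the defect is an unexplained assumption, not a miscalculation.

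*The saline arm may differ from the cited population.* Nothing in the document says that the 9% was observed under this trial's control regimen, so there may be a good reason for 10%. Statistics also says that statisticians were consulted. This stands too, but no reason is given, and the sentence itself assigns 9% to the target population.

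*The loss of power is mostly a product of the approximation.* This stands in large part. A reader might infer from the 74% that the trial has a 26% chance of missing a fall to 1%, or that 80% power from 9% would need a gentamicin rate of about 0.6%. Both are normal-approximation values. For the uncorrected chi-square test, the exact chance of missing the effect is 100 − 78.8 = 21.2%, and 80% is reached at a gentamicin rate of about 0.94%, close to the planned 1%. Nor can one say that rounding could never close the gap: the chi-square test has exact power of 82.3% at a saline rate of 9.5%, and Background gives the 9% only as approximate.

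What survives is that the stated power is not tied to the stated premise, and that its true value depends on a test the plan does not name.

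**Conclusion.** The point holds in a limited form. The sentence states one infection rate and computes from another without explanation. Under the formula that most plausibly produced the 80%, power from the 9% premise is about 74%. The exact power of the uncorrected chi-square test is 85.4% from 10% and 78.8% from 9%, so for that test the real shortfall against 80% is about 1 point; for Fisher's exact test it is about 12 points. The type 2 error is mislabelled, with no numerical effect.

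These figures assume a two-sided 0.05 level, an unadjusted comparison and 100 analysed patients per group. The choice of formula is inferred from agreement with the stated 80%. The adjusted analysis outlined in Study Design is not specified closely enough for its power to be computed.

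A reader might go further and conclude that the sample size is wrong or that more patients are needed. The documents do not support that: 100 per group is right for the rates printed beside it, and they do not establish that 9% is the correct control rate. Severity is minor to modest.

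**What to change.** Leave enrolment unchanged and rewrite the power sentence so that it:

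1. uses one saline rate throughout and, if that is 10%, says why it exceeds the cited 9%;
2. names the test and its sidedness;
3. writes the type 2 error as 0.20 wherever 80% power is stated;
4. gives power at both saline rates and says how it was calculated.

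For example: *With 100 evaluable patients per group, two-sided type 1 error 0.05 and an uncorrected chi-square test, power to detect a reduction to 1% is about 80% from a 10% saline rate and about 74% from 9% by the normal approximation (85% and 79% by exact enumeration).*

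If another test was used or is intended, name it and give its own pair of figures; for two-sided Fisher's exact test they are about 77% and 68%.

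The cost is one reworded sentence and a slightly less favourable stated power at 9%. If 10% is kept, a short justification must also be written. No patients are added and trial conduct does not change.
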